#### **11.10.2.2.1 Hematological Adverse Events of Special Interest Confirmatory Monitoring**

When an event is identified as meeting the pre-specified criteria for decrease from baseline in a laboratory sample at a post-randomization visit (sample 1) and confirmed in a second consecutively drawn sample (sample 2), the following additional monitoring will be put into place. Confirmation is defined as a repeat value that 1) meets the magnitude of decrease criterion from baseline relative to sample 1 and 2) that does not show a meaningful increase relative to sample 1. Baseline for this purpose is defined as the lowest of the available pre-randomization values.

If the decrease is confirmed, additional weekly samples for the ensuing 2 weeks (sample 3 and sample 4) will be collected (making a total of 4 samples over approximately 4 weeks) to ensure that parameters remain stable and do not go below pre-specified thresholds (see below) for discontinuation. During this monitoring, the patient may remain on study drug provided each of the following conditions are met:

- The observed values for all samples for the parameter in question remain above the following thresholds
  - 11.5/13.0 g/dL (Female/Male) for hemoglobin and at least 1 g/dL decrease from baseline
  - 2500/mm^3 for white blood cell count
  - 1250/mm^3 for neutrophils
  - 100,000 mm^3 for platelets
- There is not, in sample 2, 3, or 4 a further decrease relative to sample 1 in the measure being monitored
  - > 2 g/dL if the measure of interest is hemoglobin
  - > 500/mm^3 if the measure of interest is neutrophils,
  - > 1500 mm^3 if the measure of interest is white blood cell count,
  - > 50,000/mm^3 if the measure of interest is platelets.

- After samples 2, 3, and 4 have been obtained, and if no decrease relative to sample 1 meeting the criteria described in the above bullets has been observed, the patient may continue in the study on the usual visit schedule and the AESI is considered resolved.

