- In the event samples 2, 3 and 4 show a further decrease from sample 1 that exceeds the above criteria for the relevant measure, drug administration is halted. A repeat laboratory sample should be obtained within one week. Provided this repeat sample shows an increase from the value among sample 2, 3 or 4 that triggered the halt, study drug may be reinstated, with weekly monitoring of the relevant parameter for at least 2 samples to ensure that values remain above 100,000/ $\mu$ L for platelets, 1250/mm^3 for neutrophils and 2500/mm^3 for WBCs.

Confirmed Events of Special Interest are recorded in the EDC system by completing the AE form electronically and indicating the event as an AE of Special Interest. Since these protocol defined AESIs are intended for safety monitoring, they may not be considered untoward medical events and their monitoring should not be used to infer relationship to drug.

When a patient is discontinued, best efforts should be made by the Investigator to complete final safety assessments and follow ongoing AEs until resolution or no longer of clinical concern.

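### Two wording errors in the haematology drug-halting rules (Protocol 11.10.2.2.1): the halt sentence literally needs all three samples to breach, and a 1 g/dL haemoglobin fall is listed as a condition for staying on drug

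*Protocol*

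**What the plan says.** Protocol 11.10.2.2.1 applies once a fall in haemoglobin, white cells, neutrophils or platelets has been seen (sample 1) and confirmed (sample 2). Confirmation requires, among other things, a repeat value "that does not show a meaningful increase relative to sample 1". After that, "additional weekly samples for the ensuing 2 weeks (sample 3 and sample 4) will be collected".

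During this monitoring "the patient may remain on study drug provided each of the following conditions are met". The list that follows contains:

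- Floors that every sample must stay above. The haemoglobin floor is 11.5 g/dL (female) or 13.0 g/dL (male), and the line carries an added clause: "for hemoglobin and at least 1 g/dL decrease from baseline".
- A condition on further falls: "There is not, in sample 2, 3, or 4 a further decrease relative to sample 1 in the measure being monitored". The limits are more than 2 g/dL for haemoglobin, 500/mm³ for neutrophils, 1500/mm³ for white cells and 50,000/mm³ for platelets.
- A closing rule that returns the patient to the usual schedule: "After samples 2, 3, and 4 have been obtained, and if no decrease relative to sample 1 meeting the criteria" has been observed.

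The halt sentence then reads: "In the event samples 2, 3 and 4 show a further decrease from sample 1 that exceeds the above criteria". A repeat sample is due within one week, and drug may be restarted on this condition: "Provided this repeat sample shows an increase from the value among sample 2, 3 or 4 that triggered the halt".

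Section 11.10.2.2 gives two anaemia triggers: a fall from baseline of more than 2 g/dL, or a fall of at least 1.0 g/dL that takes the value below the floor.

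**The concern.** These lines decide whether study drug is stopped for adverse events of special interest, and about 50 sites have to apply them alike.

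The halt sentence joins the samples with *and*, while the lines around it use *or*. A site working from the halt sentence alone would wait for three breaches. A site working from the conditions list would act on one. The repeat sample and the restart step both hang on the halt, so their trigger is unclear too.

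In the haemoglobin line, a fall that Section 11.10.2.2 treats as part of the harm has become something the patient must show in order to stay on drug. Read literally, the line counts recovery against the patient.

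**Working it through.** The plan states no figure to reproduce here. The check is of logic, with simple arithmetic. All patient values below are illustrations set against the protocol's own limits.

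**1. Halt sentence against stay-on-drug condition**

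Each of samples 2, 3 and 4 either breaches the further-fall limit or does not, giving 2³ = 8 patterns.

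- Any breach (the stay condition fails): 8 − 1 = 7 patterns.
- All three breach (the halt sentence is literally met): 1 pattern.
- Permission ended but halt sentence not met: 7 − 1 = 6 patterns.

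Platelet example: baseline 300,000/mm³; samples 1 to 4 are 240,000, 180,000, 235,000 and 240,000. All are above the 100,000 floor.

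- Entry: 300,000 − 240,000 = 60,000, more than 50,000.
- Confirmation at sample 2: 300,000 − 180,000 = 120,000, with no rise over sample 1.
- Further falls from sample 1: 240,000 − 180,000 = 60,000 (breach); 240,000 − 235,000 = 5,000; 240,000 − 240,000 = 0.

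The stay condition fails at sample 2. The halt sentence, read literally, is never met. Because samples 3 and 4 follow weekly, an all-three rule could be judged only about 2 weeks after sample 2.

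**2. Haemoglobin line**

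Sample 2 cannot be a recovery, because confirmation rules that out. The literal clause can therefore first fail at sample 3.

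| | Baseline | Samples 1, 2, 3 (g/dL) | Falls from baseline | Floor |
|---|---|---|---|---|
| Female | 14.0 | 11.9, 11.8, 13.2 | 2.1, 2.2, 0.8 | 11.5 |
| Male | 16.0 | 13.9, 13.8, 15.2 | 2.1, 2.2, 0.8 | 13.0 |

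Both patients enter on a fall of more than 2 g/dL, and every value is above the floor. The largest further fall from sample 1 is 0.1 g/dL, against a limit of more than 2. Each misses the literal clause at sample 3 only because 0.8 is less than 1. Once sample 4 is in, the closing rule applies and makes no mention of the clause, so about 1 week is at stake.

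**3. Does deleting the clause remove protection?**

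- *Sample 1 above the floor.* The second trigger needs a value below the floor, so this patient entered on a fall of more than 2 g/dL. Baseline therefore exceeds 11.5 + 2 = 13.5 (female) or 13.0 + 2 = 15.0 (male). Any later value at or below the floor is already more than 2 g/dL below baseline, so a 1 g/dL requirement adds nothing.
- *Sample 1 below the floor.* The floor condition fails at once, with or without the clause.

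A grid in 0.1 g/dL steps agrees. It takes baseline from the floor to 18.0, sample 1 from 6.0 and the later value from 6.0 to baseline, keeping entries with sample 1 above the floor. It compares the floor alone with the compound rule (at or below the floor with a fall of at least 1 g/dL). There were 0 differences in 105,600 female and 48,575 male combinations.

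**The case against.** The strongest reply is that the section corrects itself. The conditions list, the closing rule and the restart sentence all work on a single breach, and the last speaks of one value that triggered the halt. The *and* can also be read as naming the set of samples under review. On the haemoglobin line, the lead-in speaks of thresholds, so the natural reading is that the patient must not reach the compound anaemia criterion of Section 11.10.2.2. The list cannot be parsed strictly in any case, since its later bullets are not conditions. Central laboratory alerts reach Investigators and the Medical Monitor (Section 11.10.1.1), and the Investigator may stop drug on clinical judgement (Section 7.7).

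Much of this stands, and it limits the point. A reader might infer that the protocol permits dosing until three samples have breached. It does not: permission ends at the first breach, and the 2-week delay arises only where a site follows the halt sentence alone. A reader might also infer that the protocol orders drug stopped in a recovering patient. It does not: the section's halt sentence requires a further fall from sample 1, which that patient does not have. At most the conditional permission lapses, and many sites would read past it.

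What does not stand is leaving the text alone. That the intended meaning can be recovered does not make the sentences right. Alerts still need a single rule to apply, and discretion to discontinue does not help a patient whose permission lapses on recovery.

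**Conclusion.** Both lines are wrong as written, and the severity is minor. The first is a contradiction within one section. Its consequence is possible inconsistency between sites and an unclear trigger for the halt, repeat-sample and restart steps; it gives no licence to keep dosing. The second is a misplaced clause that, read literally, withdraws permission for about a week from a patient who recovers to within 1 g/dL of baseline at sample 3.

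The conclusion rests on the literal wording and on reading the 1 g/dL figure as carried over from the anaemia trigger in Section 11.10.2.2. How often either situation would occur cannot be estimated from the documents. No efficacy analysis, sample size or alpha is affected.

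**What to change.** Make two edits in Protocol 11.10.2.2.1.

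1. Reword the halt sentence along these lines: *If any one of samples 2, 3 or 4 falls further from sample 1 by more than the limit for that measure, drug administration is halted.*
2. In the haemoglobin line, delete everything after the word *hemoglobin*, leaving the sex-specific floors alone.

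The cost is two wording changes in one section, with no added tests, visits or patients.

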## **12.0 ADMINISTRATIVE AND REGULATORY OBLIGATIONS**

### **12.1 Confidentiality**

#### **12.1.1 Confidential and Proprietary Information**

All information regarding the nature of the proposed investigation provided by the Sponsor to the Investigator (with the exception of information required by law or regulations to be disclosed to the IRB, the patient, or the appropriate national or local authorities) must be kept in confidence by the Investigator. The Investigator may share the information with study personnel under his/her direct supervision only for the purposes of conducting the study.

#### **12.1.2 Publication and Media Inquiries**

All manuscripts or presentations based upon this study, including press statements and internal public notices and memoranda, must be submitted to the Sponsor for review and approval prior to release for publication or presentation. This review is necessary to ensure that proprietary, non-public information is protected in accordance with confidential disclosure agreement terms between the Sponsor and the Investigator.

During and after this study, the Investigator may receive inquiries from reporters or financial analysts. Investigators are to refer these inquiries to the Sponsor for disposition.

#### **12.1.3 Patient Identity and Protected Health Information**

In accordance with 45 CFR 160 and 164, Investigators must ensure that all information regarding the health of participating patients, including information generated during the course of this

study, is maintained in such a manner so as to prevent improper disclosure. Without prior authorization or waiver, information may not be released unless it has been edited to remove any and all identifiers (eg, names, addresses, contact information, dates of birth, social security numbers, medical record numbers, and all dates with the exception of year) that would allow for data to be linked to a specific individual. As a result, Investigators must provide a privacy notice to each study patient and obtain a release waiver as described below.

For data analysis and reporting purposes, the patient will be asked to sign an authorization for release and use of protected health information as part of the initial informed consent process. This authorization will allow the Investigator to make study results available to the Sponsor and its designated representatives, as well as applicable regulatory authorities, without first removing all unique identifiers (eg, dates of birth important to establishing the eligibility of patients). However, in any communications of data for this study, patients will be identified only by their initials and a unique study identification number.

## **12.2 Independent Review Board**

The study protocol, ICF, and any other information that will be presented to study patients must be approved initially, and reviewed at least annually, by an IRB constituted in accordance with 21 CFR 56 and ICH E6 GCP guidelines. A copy of the initial IRB approval letter must be submitted to the Sponsor prior to study initiation. Investigational product will not be released to an Investigator without an assurance that final IRB approval has been granted. Subsequently, copies of all IRB correspondence should be submitted to the Sponsor on an ongoing basis.

## **12.3 Patient Recruitment and Informed Consent**

### **12.3.1 Patient Referrals**

Referrals are often an essential part of patient recruitment. Referrals to an Investigator can provide patients with access to investigational agents otherwise unavailable to the referring physician. It is important that the process of referring a patient to the Investigator conducting the study meets the requirements of ICH E6 GCP and 45 CFR 160 and 164 regarding the release of protected health information. Prior to referral, the patient should be asked if consent is given to share contact information and details of the medical condition with the Investigator. This consent should be documented by the referring physician.

### **12.3.2 Informed Consent and Other Written Information for Patients**

The ICF and any other written information for patients should meet local requirements of language and interpretation. One copy of the signed ICF and any other written information will be given to the patient and the original will be retained by the Investigator in the study files. The ICF must include eight basic elements (purpose/scope/duration, risks/discomforts, benefits, available alternative procedures/treatment, confidentiality, compensation for research-related

injury, voluntary participation/withdrawal, and contact information) in accordance with 21 CFR 50.

#### **12.4 Study Documentation**

All data relevant to the assessments outlined in this protocol must be entered in the patient's record and the EDC system. Electronic data entered for each patient will be verified by comparison to source documents (medical records, study worksheets, diagnostic reports, ECG tracings, etc) at the study site by the designated study monitor. The Investigator must make patient data accessible to the designated study monitor, to other authorized representatives of the Sponsor, and to regulatory agency representatives. At the conclusion of the study, an electronic copy of each patient's case record in the EDC system will be provided to the Investigator for retention in the study file.

According to GCP, essential documents should be retained for at least two years after the last approval of a marketing application in an ICH region and until there are no pending or contemplated marketing applications in an ICH region. In addition, records should be retained for at least two years after the formal discontinuation of clinical development of an investigational product. These documents should be retained for a longer period, however, if required by local regulatory requirements or through an agreement with the Sponsor. No study documents will be destroyed or moved to a new location without prior written approval from the Sponsor. If the Investigator relocates, retires, or withdraws from the clinical study for any reason, responsibility for the records should be formally transferred to an agreed-upon designee.

#### **12.5 Protocol Compliance**

Substantive changes in the protocol include alterations that affect the safety of patients or that alter the scope of the investigation, the scientific quality of the study, the experimental design, doses, assessment variable(s), the number of patients treated, or the patient selection criteria. These changes must be implemented via formal written protocol amendment only upon joint approval by the Sponsor and Investigator. Additionally, a protocol amendment must be reviewed and approved by the IRB prior to implementation. If a protocol amendment results in changes to the ICF, the revised form must also be approved by the Sponsor and the IRB prior to use.

Emergency departures from the protocol that eliminate an apparent immediate hazard to a particular patient, and that are deemed crucial for the safety and wellbeing of that patient, may be instituted for that patient only. The Investigator or other attending physician will also contact the Sponsor as soon as possible in the case of such a departure. These departures do not require pre-approval by the IRB; however, the IRB and the Sponsor must be notified in writing as soon as possible after the departure occurs. Furthermore, the Investigator will document in the patient's record and the electronic case report form (eCRF) the reasons for the departure from the protocol and the ensuing events.

## **12.6 Investigational Drug Accountability**

It is the responsibility of the Investigator to ensure that proper procedures are implemented with regard to the receipt, storage, and dispensation of the investigational product(s). Shipping receipts, dispensing records, and inventory forms will be examined and reconciled periodically and at the end of the study by the designated study monitor. Both the study drug used during the course of the study and any remaining unused study drug must be accounted for on the Accountability Log provided to the Investigator by the Sponsor.

## **12.7 Study Monitoring**

The designated study monitor will review the progress of the study as frequently as is necessary to ensure proper study conduct and accurate data collections through:

- Periodic on-site visits;
- Frequent telephone communications with the site; and
- Ongoing review of eCRF entries, clinical records, and administrative documents.

All records pertaining to the study will be made available to the study monitor during each site visit. To allow adequate time to assemble all of the records, visits will be confirmed well in advance whenever possible.

A separate Clinical Monitoring Plan will be prepared by the Sponsor and the designated clinical monitoring/site management CRO, which will include detailed guidance for site visit frequency, site-based data review and verification requirements, investigational product and essential document review, safety surveillance, remote eCRF data review, communications, and documentation (including reports of monitoring activity).

## **12.8 Reports**

The Investigator shall make accurate and adequate written progress reports to the IRB at appropriate intervals, not exceeding one year.

The Investigator shall make an accurate and adequate final report to the IRB within 3 months after completion or termination of the study.

The Investigator shall immediately make an accurate and adequate special report to the Sponsor and the IRB (as applicable) for any serious adverse experience.

The Sponsor will prepare a final study report within a reasonable time frame after the data from the last completed patient has been tabulated. The final approved report will then be submitted to the appropriate regulatory authorities.

## 13.0 COVID-19 RISK MITIGATION

In March 2020, COVID-19, caused by infection with SARS-CoV-2, was characterized as a pandemic by the World Health Organization. The COVID-19 pandemic impacted clinical studies worldwide due to quarantines, site closures, travel limitations, diversion of resources, and/or general interruptions in study-related procedures.

### 13.1 Risk/Benefit Assessment in the Context of COVID-19

In general, the DPN population possesses moderate risk of serious complications from any infection or febrile illness because the underlying condition of diabetes and possible complications of cardiovascular disease may pose risk for worse outcomes and complication associated with COVID-19. The emergence of COVID-19 crises increases the overall infection risk in affected communities, including DPN patients who reside in those communities.

Participation in a clinical trial provides patients with increased access to healthcare resources and reinforcement of appropriate practices during a time of increased infection risk. Study patients will have access to healthcare professionals on a more intensive schedule than a normal clinical practice for the management of DPN.

To mitigate any risk of COVID-19 infection associated with study participation, this protocol provides flexibility for conducting remote visits (through telemedicine and/or home health visits) that will maintain patient access to healthcare resources while limiting any infection risk associated with study participation.

### 13.2 Remote Visits

In response to COVID-19 situations, remote visits consisting of telemedicine and/or home health visits may be conducted in lieu of certain in-clinic visits. The exceptions are the Screening visits and the baseline visit (Day 1), which must be conducted in the clinic. [Table 3](#) specifies which activities can be conducted by a home health nurse or via telemedicine and which activities must be conducted in the clinic.

**Table 3: Categorization of Study Activities**

Remote Visits		In-Clinic Only Activities
Home Health Nurse Activities	Telemedicine Activities	
Obtain samples for the following labs: 

• Pregnancy test

• Clinical safety labs

	Review study diary/drug adherence Review new/ongoing AEs	Screening visit assessments Pain Observation Day -14 assessments

Vital signs
 
12-lead ECG
 
Confirm patient completion of patient-reported outcome measures:
 
 
• Brief Pain Inventory Short Form (pain interference section only)
 
• Neuropathy Total Symptoms Score – 6
 
• Norfolk Diabetic QOL-DN
 
• Patient Global Impression of Change
 
	
Review concomitant medications
 
Limited physical exam including skin integrity and wound healing, if applicable
 
Dispense study treatment (direct-to-patient shipping of study treatment)
 
Study treatment accountability
 
Confirm patient completion of patient-reported outcome measures:
 
 
• Brief Pain Inventory Short Form (pain interference section only)
 
• Neuropathy Total Symptoms Score – 6
 
• Norfolk Diabetic QOL-DN
 
• Patient Global Impression of Change
 
• C-SSRS
 
	
Day 1 (Pre-Treatment baseline) assessments
 
UENS
 
Physical exam including skin integrity and wound healing, if applicable
 
Intraepidermal nerve biopsy

---	--	---

If a physical exam cannot be performed in the clinic, a limited physical examination should be performed via telemedicine.

AE = adverse event; ECG = electrocardiogram; QOL-DN = Quality of Life-Diabetic Neuropathy; C-SSRS = Columbia Suicide Severity Rating Scale; UENS = Utah Early Neuropathy Scale.

If a site closes or a patient resides in a location where a shelter-in-place order is issued, the Investigator must consult with the Medical Monitor to determine the best course of action, particularly for those patients who have not yet completed the baseline visit. For patients that have completed the baseline visit, remote visit activities can proceed as outlined in [Table 3](#). A combination of home health visit and telemedicine activities may be used. If in-clinic visits are no longer possible, activities categorized as in-clinic-only activities will not be conducted. If the shelter-in-place order is lifted after a missed clinic visit, attempts should be made to conduct the missed in-clinic-only activities via an unscheduled visit.

If a patient or a member of the patient's household is suspected or confirmed to have COVID-19, the Investigator must consult with the Medical Monitor to determine the best course of action. In this situation, only telemedicine activities can proceed. If the patient misses in-clinic visits during this time, an unscheduled visit will be conducted once the patient or member of his/her

household no longer has suspected or confirmed COVID-19. At a minimum, safety labs must be performed at the unscheduled visit. Patients cannot go more than 12 weeks or 2 consecutive visits without labs being drawn.

For scenarios not delineated here or for further clarification, the Investigator should consult the Medical Monitor to determine the best course of action.

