## **9.6 Safety Extension (Week 12 to Week 24)**

From Week 12 to Week 24, all patients will receive ricolinostat 120 mg daily. Patients will return to the clinic as outlined in the schedule of events and at each visit procedures specified in the schedule of events for that visit will be performed.

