## 5. **Database lock and unblinding**

### 5.1. **Blinded data review (BDR) review of selected data prior to database lock**

The clinical database will undergo a “soft lock” when the last patient that is still in the randomized control period has completed their Week 12 visit or early study discontinuation. During the soft lock, all variables will be locked for changes except for those variables that will continue collection during the 12-week open label period (e.g., adverse events, laboratory assessments, IENFD, etc.); the data from these variables will be locked for all records collected

prior to and through the Week 12 visit. To avoid inadvertent unblinding, any data collected after Week 12 during the open label period will remain unlocked, excluded from analysis, and blinded with respect to treatment group assignment.

After the soft lock and prior to accessing the randomized treatment assignments, a review of locked blinded data will occur to accomplish the following objectives: 1) assess the impact of missing data on study analysis, 2) assess and correct the database for inconsistent data, 3) identify the per-protocol population and, 3) finalize the methods needed for analysis of the study objectives while still blinded to results. Outputs consisting of tables, listing, and figures without treatment groups or with randomly generated treatment group assignments will be produced, as needed, to accomplish the blinded data review.

A second (unblinded) data review may occur after the final patient has completed the Week 28 visit or early study discontinuation. The data collected after the initial soft lock will be analyzed during the second data review. The procedures and objectives for this data review are the same as those described above after study completion of the randomized control period.

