#### 6.1.4. *Visit windows*

Analysis visits and their windows are defined using derived study day (Section 6.1.3) instead of relying on visit labels in the clinical database because clinical visits may occur outside protocol-specified windows. Study day and days after last dose are calculated using the actual date of each scheduled and unscheduled assessment and compared to the target for each analysis visit as specified in Exhibit 4.

If a parameter is assessed or measured more than once within a visit window, the one that is closest to the protocol-scheduled time point (i.e., target) is used for the purposes of data analysis and summary. If two assessments are equidistant from a target, the earlier assessment is used. If the visit used for analysis includes two assessments on the same day, the average of the two measurements is used.

Records from visits not closest to the target study day, and therefore not used in analyses, are presented in by-subject data listings.

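### After a remote Week 12 visit, a make-up UENS may be taken on open-label ricolinostat, and the SAP's rules conflict on whether that score counts

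*Protocol*

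**What the plan says.** **Remote conduct.** Protocol 13.2 allows remote visits in response to COVID-19. "The exceptions are the Screening visits and the baseline visit (Day 1), which must be conducted in the clinic". Table 3 adds the Day -14 assessments to the in-clinic list. Week 12 is not on it, and the text after Table 3 says "For patients that have completed the baseline visit, remote visit activities can proceed as outlined in" that table.

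**UENS and drug supply.** Table 3 makes UENS in-clinic only. It lists "Dispense study treatment (direct-to-patient shipping of study treatment" among the telemedicine activities. Where clinic visits are no longer possible, "activities categorized as in-clinic-only activities will not be conducted". Once a shelter-in-place order lifts, "attempts should be made to conduct the missed in-clinic-only activities via an unscheduled visit". After a suspected or confirmed COVID-19 case in the household, only telemedicine proceeds. An unscheduled visit follows, with safety labs as the stated minimum.

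**Treatment at Week 12.** Protocol 9.6.1 puts both UENS and dispensing in the Week 12 visit, and 9.6 states "From Week 12 to Week 24, all patients will receive ricolinostat 120 mg daily".

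**Analysis.** UENS change at Week 12 is the second key secondary endpoint, tested last in the fixed sequence (SAP 8.2). SAP 6.1.4 says "Study day and days after last dose are calculated using the actual date of each scheduled and unscheduled assessment". Exhibit 4 sets the Week 12 window at 14 to 32 days after last dose, with target Day 84. SAP 5.1, on the lock after the randomized period, says "any data collected after Week 12 during the open label period will remain unlocked, excluded from analysis". SAP Table 9, the UENS estimand, deals with treatment and study discontinuation and does not mention the start of open-label drug.

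**The concern.** At a remote Week 12 visit the examination has to wait but the drug does not. The documents allow open-label ricolinostat to reach the patient first and then ask for the UENS later. They set no latest day and no condition on the first open-label dose.

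This matters most in the placebo arm. A placebo patient examined after starting open-label drug is no longer a placebo observation, while a ricolinostat patient has only had longer exposure. The schedule of assessments has one post-baseline UENS in the double-blind period, at Week 12, so no earlier on-treatment score can stand in for it. The SAP does not give a single answer on whether the late score is used, and the two answers lead to different problems: dilution of the difference, or a missing value.

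**Working it through.** **1. Which score would the SAP select?** The Week 12 visit falls on Days 82 to 86, so take the last double-blind dose to be on Day L = 82 to 86.

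- Window = L + 14 to L + 32. For L = 82 this is Days 96 to 114; for L = 84, Days 98 to 116; for L = 86, Days 100 to 118.
- An on-time UENS is about 0 days after that dose, so it falls outside the window.
- A make-up UENS on Days 96 to 118 falls inside. If open-label dosing began promptly, that is 2 to 4.6 weeks (14/7 to 32/7) into ricolinostat.
- If *last dose* means the final dose of study drug, at about Day 168, the window is Days 182 to 200. No Week 12 score from a completer falls in it. Exhibit 4 gives the Week 26 row the same window text.

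So 6.1.4 with Exhibit 4, read with the last double-blind dose, would take the late score and reject the on-time one. SAP 5.1 would reject the late one.

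**2. The plan's own sample size.** Inputs from Protocol 10.3.1 and 10.3.3: difference 0.8, SD 2.35, two-sided alpha 0.05, power 0.80, 1:1 allocation.

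- d = 0.8/2.35 = 0.340.
- Normal approximation: n = 2(1.96 + 0.8416)²/d², giving 136 per arm (272 in total).
- t-test: 136.4, rounded up to 137 per arm, or 274. This matches the plan.

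These figures are for the NRS. No effect size or power is stated for UENS, so the same design is borrowed below purely as a test with about 80% power.

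**3. Late scores used.** Let f be the share of placebo patients whose Week 12 UENS was taken after open-label start and used. Let g be the share of the drug effect present by then. The difference becomes d(1 − f·g), and power = Φ(d(1 − f·g)·√(137/2) − 1.96). With f = 0 this is Φ(2.818 − 1.96) = 80.4%.

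| f | g = 0.25 | g = 0.5 | g = 1 |
|---|---|---|---|
| 5% | 79.5% | 78.4% | 76.3% |
| 10% | 78.4% | 76.3% | 71.8% |
| 20% | 76.3% | 71.8% | 61.6% |

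The smallest loss is 80.4 − 79.5 = 0.9 points and the largest is 80.4 − 61.6 = 18.8 points.

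**4. Late scores dropped, nothing recovered by imputation.** Both arms lose f, so n = 137(1 − f) and d is unchanged. Power is 78.4%, 76.2% and 71.2% for f = 5%, 10% and 20%, a loss of about 2 to 9 points.

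**5. Late scores dropped, ricolinostat values imputed from placebo.** The difference shrinks by f, which gives the g = 1 column above. This branch requires reference-based imputation for a patient who never discontinued (see the objection).

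All of these are for the UENS test taken alone, before allowing for its place in the sequence.

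**The case against.** The documents permit this sequence but do not require it. A reader might infer that open-label drug has always been shipped and taken before the make-up examination. Section 13.2 says only that remote activities can proceed, in consultation with the Medical Monitor, and a UENS done before the first open-label dose is clean.

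A reader might also take 9.6.1 to place UENS ahead of dispensing, so that the remote route reverses a set order. That section is an unordered list. Where the protocol wants an order it states one, as in Table 1 footnote 14 for Day 1. Nor does the safety-labs wording bar a UENS at the post-COVID visit; it sets a floor.

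A dropped score should not be assumed to be imputed at the placebo mean. Table 9 reserves reference-based imputation for values missing because of treatment or study discontinuation, and a continuing patient has done neither. That points to imputation under MAR within the assigned arm, and so to lost information rather than shrinkage. Some ambiguity remains: SAP 6.1.5.2 sends every value that is not intermittent to reference-based imputation, and *intermittent* is hard to apply to a single double-blind visit.

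SAP 5.1 already leans toward exclusion, its blinded review can finalize methods, and Protocol 13.4 has COVID-related deviations captured and discussed in the study report. Exhibit 4 is labelled an example. These points reduce the risk, but none supplies a rule for this score. SAP 5.1 addresses what is held back at the first lock and does not define the Week 12 UENS.

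Finally, g = 1 is severe: Protocol 7.2 itself expects that the full effect in patients could take longer to appear.

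**Conclusion.** The gap is real. The protocol does not tie a make-up UENS to the first open-label dose, SAP 6.1.4 with Exhibit 4 conflicts with SAP 5.1 on whether a late score counts, and the estimand does not name the open-label start. One literal reading puts placebo patients scored on ricolinostat into an alpha-controlled endpoint. The bias is toward zero. If the drug has no effect there is nothing to dilute, so this does not by itself inflate false positives.

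The size cannot be determined. The documents give no number of remote Week 12 visits, no UENS effect and no onset time. Under assumed shares of 5% to 20%, using late scores costs about 1 to at most about 19 power points, and the top figure needs both a 20% share and the full drug effect by the make-up date. Dropping them under MAR with nothing recovered costs about 2 to 9. The relevant share is the patients who were remote, already dosed and examined late, so it cannot exceed the remote share.

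This is a contingency affecting the last-tested endpoint of a Phase 2 trial. It still warrants a rule set before unblinding, because the correction is short and the existing rules disagree.

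**What to change.** - **SAP 6.1.4, Exhibit 4 and Table 9:** state that a UENS counts as Week 12 only if dated on or before the first open-label dose, and record that dose date. List later scores without analysing them as Week 12. Name open-label start before UENS as an intercurrent event.
- **SAP 6.1.5.2 and Table 9:** state that the resulting missing value is imputed under MAR within the assigned arm when the patient has not discontinued.
- **Exhibit 4:** correct the Week 12 window so that on-time scores fall inside it. The rule above does not repair this on its own.
- **Protocol 13.2:** ask sites to obtain the make-up UENS before the first open-label dose where a clinic visit allows, and name UENS alongside safety labs for the post-COVID visit.

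Protocol 9.6, 9.6.1 and 13.2 with Table 3, and SAP 5.1, 6.1.4, Exhibit 4, 6.1.5.2 and Table 9, must be reconciled. This concerns which examination counts and when it is scheduled; it sets no rule on shipment or dosing.

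The cost is a few sentences in each document. A few late scores go unused, and some Week 12 clinic visits need closer scheduling. The scheduling request will help few patients while clinics are closed, so the dated cut-off is the main protection.
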